Key Inclusion Criteria:	
Education: Enrollment and completion of all study-related activities in one of the parent studies; complete and interpretable PET amyloid data (tau data recommended but not required); for participants with Dementia – Alzheimer's Type (DAT), the presence of a co-participant is required; for participants with Mild Cognitive Impairment (MCI), co-participants are strongly encouraged unless the participant has a legally authorized representative or power of attorney for medical/research decisions; for those completing virtual visits: laptop, desktop, or tablet (>9.7" diagonal width) and stable, secure internet connection required; prior established relationship with a PCP, geriatrician, or mental health professional.
 
Disclosure: Same as Education portion, plus requirement for demonstrated intact decisional capacity for PET amyloid and tau disclosure

Key Exclusion Criteria:	
Education: Baseline severe or untreated active depression/anxiety or other severe psychological diagnosis, other significant neurological insult or diagnosis, severe and untreated substance use disorder, severe hearing or vision impairment
 
Disclosure: lack of participant/designated other decisional capacity

Study Type:	Interventional, single-group design
Primary purpose:	
Education: Complete educational presentation about Alzheimer's Disease (AD), Dementia-Alzheimer's Type (DAT), amyloid and tau PET imaging as it relates to AD diagnosis, and risks and benefits of learning this personal health information; measure comprehension and decisional capacity for PET disclosure among symptomatic participants and/or their co-participants.
 
Disclosure: Complete personalized PET amyloid and tau disclosure protocols with participants and family members of diverse racial-ethnic backgrounds; investigate initial outcomes including comprehension/recall of results, positive and negative psychological reactions, perceived disease stigma, and future time perspective immediately following disclosure, within 1-week post-disclosure, and at 6-weeks post-disclosure

Phase:	I/II (Part II: Disclosure)
Date of First Enrollment:	10/1/2020
Target Sample Size:	100
Recruitment Status:	Currently recruiting

The **central goal** of this supplement is to begin addressing a vital “communication” gap that occurs between the collection of biomarker data related to Alzheimer’s disease (AD) and related dementias and the absence of methods to disclose this information to patients and their care partners, as applicable. The longstanding justification that disclosure is not appropriate or necessary given the lack of pharmacologic treatment options is now thoroughly undermined by evidence that lifestyle¹⁻² and other non-pharmacologic interventions³⁻⁴ may alter clinical progression. Regardless of whether asymptomatic⁵⁻⁶ or symptomatic⁷⁻¹⁰, patients almost universally demonstrate strong interest in knowing their biomarker-based risk information, and seek to use this information to plan health behavior or lifestyle change^{5,11-15}. The combination of this literature and our preliminary data below demonstrate a clear benefit of, and participant interest in, knowing biomarker status. Thus, we directly address the **first ethical dilemma** that potentially impactful information is being intentionally withheld from our participants.

The current project leverages a robust recruitment and characterization pipeline formed through the Stimulation to Improve Memory study (STIM; R01AG058724) as well as empirically-derived methods from the Sharing Alzheimer’s Risk Estimates (SHARE; R03AG063222-01) study. STIM will ultimately enroll up to 240 individuals with mild cognitive impairment (MCI) and dementia of the Alzheimer’s type (DAT) to evaluate the dose-response relationship associated with transcranial direct current stimulation. Each participant receives both amyloid and tau positron emission tomography (PET), which are used as participant-specific factors that may affect tDCS efficacy. We did not include biomarker disclosure in STIM because it was outside of the scope of the intervention-related focus. Moreover, it was not clear at the time of the initial submission whether participants would be interested in receiving feedback about their biomarker status. Approximately 3 recruiting quarters into the study, there is now substantial evidence that participants **want** the information. Thus, the STIM infrastructure provides an ideal testbed for developing/refining feedback methods for cognitively symptomatic individuals. To improve enrollment and in response to overwhelming interest in biomarker disclosure, we are also opening up this study to participants from other studies co-enrolling through the Michigan Alzheimer’s Disease Research Center that include PET amyloid (and tau, if available) imaging, as long as they meet other criteria detailed above. These additional ‘parent’ studies include the Driving and Physiological Responses (DAPR; HUM00183327), Brain-Behavior Characterization (BBC; HUM00200763) and Dementia in African American Population Phenotyping from Potential Elevated Risk (DAPPER; HUM00152159) studies.

We have **preliminary data**, acquired from Co-I [name]’s R03-funded study investigating older participants’ interest in biomarker-based feedback, that shows a clear majority of participants have moderate-strong interest in learning their amyloid and tau status (Table 1). In fact, these initial data indicate that participants have equal if not stronger interest in biomarker disclosure as compared to other sources of health information (Table 1). Furthermore, 100% of participants interviewed to date would elect to learn their Alzheimer’s-related biomarker status if it were available, regardless of race, gender, or whether they were cognitively symptomatic or healthy. These findings mirror preliminary data gathered from those currently

[figure not shown]
Table 1. Preliminary Biomarker Disclosure Interest Data

Interest Level	Clinical Information	Structural Neuroimaging	APO-E Genotype	Amyloid/Tau Status
No Interest	0 (0%)	0 (0%)	0 (0%)	0 (0%)
Very Minimal Interest	0 (0%)	0 (0%)	0 (0%)	0 (0%)
Neutral Interest	0 (0%)	1 (6%)	1 (6%)	0 (0%)
Moderate Interest	1 (6%)	1 (6%)	1 (6%)	2 (12%)
Strong Interest	15 (94%)	14 (88%)	14 (88%)	14 (88%)
Would you engage in elective disclosure about your risk for AD based on these variables?				
No	0 (0%)	0 (0%)	0 (0%)	0 (0%)
Yes	16 (100%)	16 (100%)	16 (100%)	16 (100%)

enrolled in STIM (in which the study team does NOT mention disclosure options): of the 31 enrolled participants, 42% spontaneously requested feedback about their amyloid and tau imaging, and 23% mentioned significant disappointment or distress that the current protocol does not allow for disclosure of this information. Additionally, two participants were previously interested in the study but declined to enroll after learning that feedback was not currently provided.

The ethical principles of patient autonomy and beneficence must be carefully weighed against non-maleficence and protection of the potentially vulnerable population of cognitively impaired older adults¹⁶. AD Biomarker disclosure can occur only if patients (or their designated signors) fully understand the information to be shared, and appreciate the risks and benefits of knowing this information. Preliminary data from Co-I [name]'s R03 demonstrate that participants request risk disclosure for a variety of perceived benefits; however, 88% endorse having 'no concerns' about risks of amyloid or tau disclosure (Figure 1). These data, while likely reflective of a strong desire for disclosure in the larger population, indicate a **second ethical dilemma**: whether to share information with symptomatic participants who may have impaired decision-making capacity to engage in amyloid/tau disclosure.

Figure 1. Participants' perceptions of primary benefits and risks of AD biomarker disclosure (data from Co-I [name]'s R03)

Finally, results of the prior literature suggest that disclosure of biomarker information related to AD is both safe and well-tolerated among cognitively healthy participants. Studies examining post-disclosure psychological reactions are very limited in individuals with mild cognitive impairment, and non-existent for individuals already diagnosed with DAT. Further, no prior study has examined the impact of symptomatic patients' biomarker information on care partners who are likely impacted by their partners' health information related to AD and who are also likely to have a pivotal role in their partners' health care and future care in the event of worsening cognitive impairment. Additionally, prior studies have exclusively considered the negative psychological effects of risk disclosure, rather than the full range of emotional reactions and the empowering results that may follow disclosure. Therefore, we address this **third ethical dilemma** by evaluating both positive (e.g., relief, happiness, satisfaction, empowerment) and negative (e.g., depression, anxiety, anger, distress) effects of biomarker disclosure on symptomatic participants and their co-participants (e.g., care partners).

SECTION 2.2: Objectives & Hypotheses of the study

Preliminary data gathered from the Stimulation to Improve Memory (STIM) study and an associated research project have highlighted several unforeseen but compelling needs in regards to sharing of Alzheimer's disease (AD) biomarker information with research participants and patients alike. The proposed ethics supplement addresses three of these needs, each of which represents an ethical dilemma underlying the communication gap in AD biomarker research: 1) the withholding of biomarker information from interested participants, 2) the unknown ability of cognitively symptomatic patients to appreciate risks and benefits of biomarker disclosure, and 3) the psychological ramifications of biomarker disclosure in cognitively impaired patients. We will leverage STIM infrastructure to systematically address these questions through three specific aims:

Aim 1 investigates interest in, and follow through with, amyloid and tau status disclosure in individuals diagnosed with MCI and DAT. At the time of study enrollment, we will offer all parent study participants the opportunity to learn their amyloid and tau status upon completion of parent study procedures; recording preference as appropriate. We will then examine follow through rates (i.e., interested vs. completed disclosures) thereby extending the literature. We predict *an equally high interest in, and completion of, disclosure regardless of diagnosis.*

Aim 2 examines whether cognitively symptomatic participants demonstrate decision-making capacity as it relates to biomarker disclosure. The question of whether research participants can demonstrate decision-making capacity for biomarker disclosure has, to our knowledge, never been addressed in cognitively symptomatic individuals. Thus, we fill a critical void by evaluating whether such “patients” adequately demonstrate the fundamental elements of decision-making capacity (understanding, appreciation, rationale, communication)¹⁷. Prior to disclosure, we will use a standardized, clinician-rated measure to evaluate capacity. *We predict a main effect of diagnosis where DAT participants demonstrate poorer decisional capacity relative to MCI.* Importantly, we overcome this predicted difference by providing disclosure to either the impaired participant’s legally authorized representative or their healthcare provider. In this way, we ensure the desired information is relayed to each interested participant while still achieving the study aims.

Aim 3 will determine immediate and prolonged psychological reactions to biomarker disclosure among participants with MCI and DAT and their respective co-participants (e.g., care partners). We will assess changes in psychological status (both positive and negative) at two time points following disclosure relative to baseline. While one could predict changes in either direction, the above noted paucity of data in this area undermine the validity of such predictions. Thus, this aim is more descriptive in nature and provides critical information about cognitively symptomatic participants’ response to biomarker disclosure that will guide future research and translational efforts.

Aim 4 examines the impact of biomarker disclosure on co-participants as it relates to caregiving readiness and self-efficacy. We will assess changes in perceived readiness to provide care (to the participant) and caregiving self-efficacy at two time points following disclosure relative to baseline among co-participants who are either currently providing care to participants with MCI/DAT or who will hypothetically take on the caregiving role should the need arise. We predict that caregiving preparedness will be associated with the participant’s disclosed amyloid/tau result; specifically, an ‘elevated’ biomarker result is hypothesized to be associated with greater caregiving preparedness. Conversely, it is hypothesized that co-participants will have lower perceived readiness for caregiving if the participant’s amyloid/tau result is ‘not elevated.’

SECTION 2.3: Trial Design

The Education portion of the study is considered a Phase I/II Behavioral Intervention clinical trial without randomization. The Disclosure portion of the study is considered a Phase I/II Behavioral Intervention clinical trial without randomization, with the disclosure feedback serving as the intervention. The study will use a single-group design. All 100 participants (and any co-participants attending the first session) will complete the educational presentation and undergo an assessment of comprehension and decisional capacity. Those participants or dyads who meet criteria and demonstrate intact decisional capacity will be offered feedback about the participant’s PET amyloid and tau results. Outcomes will be measured immediately following feedback, within one week of disclosure, and at six-weeks post-disclosure. For more information regarding design, see *Methods* section.

SECTION 3: METHODS

SECTION 3.1 Participants: Inclusion & Exclusion Criteria

The proposed supplement directly extends STIM study infrastructure (Figure 2). All participants will complete parent study procedures (including amyloid and tau PET) before engaging in the activities of this supplement.

Participants: All participants (i.e., those with MCI and DAT) enrolled in STIM (HUM00146180) will express their interest in biomarker disclosure (Aim 1); however, only those who actually complete PET imaging will be eligible to receive this information (otherwise there is no information to disclose). Specific inclusion and exclusion criteria for STIM are included below:

STIM Inclusion Criteria:

- (1) Diagnosis of MCI or DAT
- (2) Age 55 and older
- (3) MRI-compatible
- (4) Stable on medications for 4 weeks prior to study enrollment

STIM Exclusion Criteria:

- (1) Other neurologic disease (e.g., epilepsy, stroke, traumatic brain injury)
- (2) Psychiatric conditions (e.g., moderate-severe depression, bipolar disorder, schizophrenia)
- (3) Sensory impairments that limit the ability to take part in the study
- (4) A significant history of, or current alcohol or drug abuse/dependence
- (5) Are left-handed with right hemisphere language lateralization

We will additionally invite participants who have completed PET amyloid (and ideally tau) scans through other MADRC-co-enrolled studies (DAPR [HUM00183327], BBC [HUM00200763] and DAPPER [HUM00152159]) to take part in this bioethics supplement, provided they have a diagnosis of MCI or DAT and meet with the additional study-specific criteria below.

Additional inclusion/exclusion criteria for the Education portion of the study are included below:

Part I Education Inclusion Criteria:

- (1) Complete and interpretable PET amyloid and tau imaging
- (2) For those completing virtual sessions: Laptop, desktop, or tablet with 9/7" diagonal diameter and stable, secure internet connection
- (3) Established relationship with a primary care provider, geriatrician, and/or mental health professional
- (4) Co-Participant – required for individuals with DAT; strongly encouraged for participants with MCI

Part I Education Exclusion Criteria:

- (1) Baseline active depression or anxiety or clinically elevated scores on Geriatric Depression Scale – 15 (GDS-15)²⁵⁻²⁶ or Beck Anxiety Inventory (BAI)²⁷⁻²⁸
- (2) History of significant neurological disease
- (3) Current severe or untreated substance use disorder

Part II Disclosure Inclusion Criteria:

- (1) Demonstrated intact decisional capacity for amyloid and tau PET disclosure

Part II Disclosure Exclusion Criteria: No additional criteria

For the proposed study, we will offer all of the participants who have completed all parent study procedures up to and during this one-year supplement funding period (we estimate up to 100 individuals) the opportunity to enroll in the supplement-related procedures.

Co-Participants: Co-participants are required for all participants with a diagnosis of DAT, given the likelihood that participants may have impaired decision-making capacity and/or need additional support following disclosure. Co-participants are also strongly recommended, though not required, for participants with a diagnosis of MCI except in the event a participant with MCI demonstrates impaired decision-making capacity, thus requiring a co-participant. Co-participants are defined as (a) those who are currently serving as a

caregiver to the participant, or would hypothetically serve in this role should the need arise; (b) individuals who know the participant well, as demonstrated by a relationship lasting at least five years, and contact (any modality) at least once per week. Co-participants must also be age 18 years or older, English-speaking, cognitively healthy, and without current severe or untreated depression and/or anxiety.

Of note, if participants have a dedicated legally authorized representative (LAR) or durable power of attorney (DPOA) for medical and/or research decisions, this individual must serve as the co-participant in order for the participant to take part in the study. Documentation of this legal designation must be provided.

SECTION 3.2 Recruitment Strategy

Participants for Part I: Education will be recruited from parent studies via invitation only. The study team will review participants who completed the parent study, screen these cases for any interim changes that might impact eligibility of the participant (or co-participant, if there is one), and contact dyads to determine interest in engaging in STIM+ Education.

All participants who demonstrate decisional capacity for disclosure (or have a co-participant or LAR/DPOA who demonstrate decisional capacity for disclosure) will be invited to take part in Part II: Disclosure by study team invitation.

SECTION 3.3 Procedures

In light of the 2020 global COVID-19 pandemic, we have adapted our procedures to include **the option for virtual, video-conferencing sessions**, to reduce the risk of exposure for our vulnerable study population. The virtual option will be the default offered to all participants. Participants and co-participants must utilize a desktop or laptop computer, or a tablet with a screen at least 9.7 inches in diagonal width to ensure that they are able to view the materials for Part I Education and Part II Disclosure completely. Additionally, participants/co-participants must have access to a stable, secure internet connection (not public Wi-Fi) and a quiet, private space where they will be uninterrupted for the duration of their appointment(s). Those enrolled in the study will be sent private links to engage in a secure video conference session through the Zoom for Health application, a free, HIPAA-compliant service through the University of Michigan.

Participants who do not have access to or comfort with the above technology will be offered the opportunity to take part in an in-person visit following strict Covid-19 safety precautions that include preliminary, day-before, and day-of screening for symptoms using the University of Michigan ResponsiBLUE screening, PPE for participants and study team members, distancing while in the laboratory, and rigorous cleaning and contact tracing procedures. In-person visits and associated procedures will follow recommendations from the Office of Research.

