3.5.2 Statistical Design

Data Screening

Prior to statistical analyses, data screening will be conducted. Initial steps will include a missing data analysis to determine randomness of missing data and range checks to assess for data quality. Additional screening for univariate and multivariate outliers, skewness and kurtosis will be conducted to inform needs for data transformation and statistical approach.

Statistical Approach

To assess Aim 1, we will compare the proportion of individuals in each diagnostic group who request vs. completed disclosure using a chi-squared test. Similarly, we will test hypotheses associated with Aim 2 (*greater disclosure decisional capacity in MCI than DAT*) by comparing the proportion of individuals in the DAT and MCI groups who demonstrate 'pass' scores on the DDMAT using a chi-squared test. We will also explore which particular elements of decision-making capacity may be more impaired in each group by comparing proportion of each diagnostic group who can adequately demonstrate understanding, appreciation, rationale, and communication on the DMAT using the same statistical strategy. To evaluate Aim 3, (*psychological reactions based on biomarker status*) we will compare participants' and co-participants' responses on outcome measures, based on amyloid and/or tau positivity vs. biomarker negativity. As we expect outcome measures to be correlated, we will utilize a 2 (diagnosis: MCI vs. DAT) by 2 (biomarker status: positive vs. negative) repeated measures analysis of variance (rmANOVA) approach for each follow-up time point. We will also compare differences in psychological reactions between participants and co-participants by diagnosis (MCI vs. DAT) using a paired t-test on all continuous items and a chi-squared test on categorical items. To evaluate Aim 4 (*impact of biomarker disclosure on co-participant caregiving readiness and self-efficacy*), we will similarly compare co-participants' responses, based on amyloid and/or tau positivity vs. biomarker negativity. As we expect outcome measures to be correlated, we will utilize a 2 (participant's diagnosis: MCI vs. DAT) by 2 (biomarker status: positive vs. negative) repeated measures analysis of variance (rmANOVA) approach for each follow-up time point.

SECTION 4: MONITORING

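### Aim 4 pools current and hypothetical caregivers with no role term; this can bias the biomarker contrast if it is tested on levels, and a change-from-baseline test with role added would close the gap

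*Combined protocol and SAP*

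**What the plan says.** Section 2.2 (Aim 4) covers co-participants who are "either currently providing care to participants with MCI/DAT or who will hypothetically take on the caregiving role should the need arise". The co-participant definition in Section 3.1 likewise accepts someone who gives care now "or would hypothetically serve in this role should the need arise". No stratum or quota separates the two.

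The stated objective is change in readiness and in "caregiving self-efficacy at two time points following disclosure relative to baseline among co-participants". The prediction that follows is worded as a level: an elevated "biomarker result is hypothesized to be associated with greater caregiving preparedness".

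Section 3.5.2 forms the comparison groups "based on amyloid and/or tau positivity vs. biomarker negativity" and gives a two-factor model: "diagnosis: MCI vs. DAT) by 2 (biomarker status: positive vs. negative) repeated measures analysis of variance (rmANOVA) approach for each follow-up time point". Caregiving role is not a factor, covariate or subgroup. The section does not say whether the pre-disclosure score enters the model, or which term tests the prediction.

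Section 2.3 describes a single-group study without randomization. Table 4 (Section 3.4) schedules both caregiving scales, the Preparedness for Caregiving Scale (PCS) and the caregiving self-efficacy subscale, before disclosure, at 1 week and at 6 weeks.

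**The concern.** A current caregiver rates preparedness from experience; a hypothetical one rates an imagined task. Section 3.4 describes the self-efficacy scale as designed for caregivers of people with dementia, so role bears on what a score means. Role may also affect how far a score can move once a result is heard.

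Nothing in the design balances role between the result groups. If, within MCI or within DAT, current caregivers are more common on one side of the biomarker split, their typical score is carried into the biomarker contrast. An association between an elevated result and preparedness could then be created, enlarged or hidden by who already gives care. PCS and caregiving self-efficacy are primary outcomes 4.1 and 4.2, and Aim 4, unlike Aim 3, makes a directional prediction.

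**Working it through.** There is no figure in the plan to reproduce. For Aim 4 the documents give no alpha, power, effect size, SD or role split. The 100 participants are a feasibility estimate, and the number of co-participants is not stated.

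**Step 1: levels.** Let g be the share of current caregivers among elevated minus not-elevated results, within a diagnosis. Let d be the mean score of current minus hypothetical caregivers. With no disclosure effect, the spurious difference in follow-up scores is g × d. The PCS has 8 items scored 0 to 4, so it runs from 0 to 8 × 4 = 32. With assumed inputs:
- 60% vs 40%, d = 3: 0.2 × 3 = 0.6 points
- 70% vs 40%, d = 4: 0.3 × 4 = 1.2 points
- 80% vs 40%, d = 5: 0.4 × 5 = 2.0 points

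**Step 2: change from baseline.** Let c be the extra change in current caregivers. The baseline contrast is g × d and the follow-up contrast is g × (d + c), so the contrast in change is g × c. If c = 0, the middle case gives 1.2 − 1.2 = 0. The 0.6 to 2.0 point illustration therefore applies to levels only.

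**Step 3: SD units (assumed).** On levels, the range is 0.2 × 0.5 = 0.10 to 0.4 × 0.8 = 0.32 SD. On change with c = 0.3 SD, it is 0.2 × 0.3 = 0.06 to 0.4 × 0.3 = 0.12 SD.

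**Step 4: simulation.** There were 3,000 runs per scenario with no true biomarker effect, the diagnosis by biomarker model, one follow-up against baseline, and two-sided 0.05. Assumptions:
- 60 or 100 dyads, half MCI and half DAT
- 55% (MCI) and 75% (DAT) biomarker-positive
- current-caregiver share centred on 30% (MCI) and 70% (DAT)
- baseline to follow-up correlation 0.6
- g = 0.2 or 0.4 unless stated; d = 0.5 or 0.8 SD when c = 0; d = 0.5 SD when c = 0.3

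| Analysis | Bias (SD) | False positives, 60 dyads | False positives, 100 dyads |
|---|---|---|---|
| Follow-up level or biomarker main effect, c = 0 | 0.10 to 0.32 | 7 to 24% | 8 to 33% |
| Change, c = 0 | about 0 | 4.7 to 5.2% | 4.5 to 5.2% |
| Change, c = 0.3 | 0.05 to 0.13 | 6 to 8% | 6 to 11% |
| Follow-up adjusted for baseline, c = 0 | 0.04 to 0.11 | 5.5 to 7.4% | 5.6 to 9.7% |
| Follow-up adjusted for baseline, c = 0.3 | 0.09 to 0.20 | 6 to 14% | 8 to 20% |
| Any of these, g = 0 | at most 0.012 | 4.4 to 5.6% | 4.2 to 5.7% |
| Role term added, level or change | at most 0.014 | 4.3 to 5.4% | 4.3 to 5.7% |

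The Monte Carlo standard error at 5% is √(0.05 × 0.95 / 3,000) = 0.4 percentage points.

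Adding role to a model for change is the same as adding role by time to the repeated-measures model. A role main effect alone leaves the biomarker by time contrast untouched. Baseline-adjusted follow-up with a role term was not simulated. In this data model, though, expected follow-up given baseline and role does not depend on biomarker status, so the bias is zero by construction.

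**The case against.** The case against is strong, and most of it stands.

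- **Baseline is measured and the objective is change.** Both scales are taken in Part I. Section 3.5.1 says PET data are not requested until Part I is complete, and Section 5.3 says no result is fed back at that stage. A stable role difference is thus already in the baseline and cancels in change. This stands, but it protects the analysis only if change is what is tested. Section 3.5.2 does not commit to that, and the prediction in Section 2.2 is worded as a level.
- **Diagnosis is in the model.** Role differences that merely follow MCI versus DAT are absorbed. This stands; only a gap within diagnosis matters.
- **Nothing in the documents shows such a gap.** All participants are symptomatic, and a person with DAT and a not-elevated result may equally have an active caregiver. Nor do the documents say which role scores higher. This stands as to size and direction, but the gap cannot be checked unless role is recorded.
- **Other covariates could be named in a study of this size.** True, but role is the distinction the aim and the eligibility definition themselves draw.

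A reader might infer that the study does not record role at all. The data collection forms are not part of the documents, so that cannot be concluded. Nor does the definition in Section 3.1 already ask for it: either role suffices, and staff are not told to separate them.

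**Conclusion.** The pooling of roles and the absence of a role term are plain in the text. The consequence is conditional. It needs a role imbalance between result groups within a diagnosis, together with either a test on levels (or the biomarker main effect) or an effect of role on change.

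Under the assumptions shown, a test on levels gives a spurious 0.10 to 0.32 SD. A change test gives about zero if the role difference is stable, and 0.05 to 0.13 SD if role also shifts change by 0.3 SD. The signs follow from assuming that current caregivers are commoner among elevated results and score higher; if only one of these is reversed, the sign reverses.

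A reader might go further and infer that an association between an elevated result and preparedness would be an artefact of role mix, or that 0.6 to 2.0 PCS points is the bias to expect in Aim 4. The documents support neither: they give no role split, SD or direction, and on the stated objective of change those same inputs yield zero. This is a worthwhile low-cost improvement, not a flaw that invalidates Aim 4.

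**What to change.** 1. Record current versus hypothetical caregiver as a yes/no item at baseline, before disclosure. For dyads already enrolled, ask about status at the Education session and flag the answer as retrospective.
2. State in Section 3.5.2 that Aim 4 is tested as biomarker by time with the pre-disclosure score included, or as follow-up adjusted for that score. Align the wording of the prediction in Section 2.2 with the chosen test.
3. Add role as a covariate. In the repeated-measures model, also add role by time.
4. Tabulate PCS and caregiving self-efficacy by role and biomarker result at each scheduled time point.

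The cost is one form field. It also takes one degree of freedom in the baseline-adjusted model, or two (role and role by time) in a repeated-measures model of baseline and one follow-up, in a sample of at most about 100 dyads. Adjustment removes confounding by role only; the biomarker contrast remains observational.
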